#### **12.1.6. Neonatal blood glucose monitoring**

Neonatal blood glucose concentrations (BGC) will be measured after first feed at 1-2 hours of age and then pre-feed 3-4 hourly until 12 hours of age unless hypoglycaemia has occurred (continue monitoring until three consecutive blood glucose concentrations have been  $\geq 2.6$  mM). BGC should be measured using a glucose oxidase method, e.g. i-STAT analyser or blood gas analyser; if this is not available alternatives such as Accucheck should be used. Method of analysis will be noted with BGC recordings. If it is not possible to complete one or more of the recommended BGC this will be recorded in the CRF along with the reason why it was not carried out. Any additional clinically indicated blood glucose levels  $< 2.6$  mM recorded in the neonatal period will be collected. We will recommend that hypoglycaemia is treated following the ADHB Hypoglycaemia in the neonate guideline and the national Oral Dextrose Gel guideline. Surveillance and treatment algorithms will be supplied to sites (Appendix).

#### **12.1.7 Concomitant Clinical Management and Co-interventions**

Management of care and any additional therapies required will be provided at the discretion of the clinician/study site. Care of the woman during the antenatal period, labour and postnatal stay will be managed by the responsible obstetric and midwifery teams and care of the neonate will be the responsibility of the neonatology and midwifery teams. Relevant data regarding co-interventions and care will be recorded in the CRF.

#### **12.1.8 Outcome data collection**

Detailed data will be collected regarding delivery, maternal and neonatal outcomes from the maternal and neonatal records. Maternal outcome data will be collected until six weeks after birth. Neonatal outcome data will be collected until six weeks after birth.

To allow for later economic analyses, cost weight scores; clinical codes; and diagnostic sequences from the New Zealand National Minimum Dataset (NMDS) for mother and baby will be collected from health records and/or the Ministry of Health. In Australia Medicare data will be obtained from the federal government via the Health Insurance Commission. The Medicare system provides reimbursement for pharmaceutical benefits schedule (PBS) and medical benefits schedule (MBS) health care costs incurred by individuals within Australia.

#### **12.1.9 Post-partum questionnaires**

Participants will be sent the following questionnaires six weeks after delivery via email (or postal hard copy if requested):

- The SF-36 quality of life questionnaire to assess overall health and wellbeing.
- The Edinburgh Postnatal Depression Scale (EPDS) to assess mental wellbeing.
- C\*STEROID Trial 6 week follow up questionnaire.

The EPDS will be reviewed centrally once questionnaires are returned. Questionnaires completed electronically by the participant will be scored automatically. The REDCap database

will send an immediate notification to the Auckland coordinator for any questionnaires where the overall EPDS score  $\geq 13$  or item 10 is marked as yes; the local site investigator, research midwife, participant's LMC or GP will then be contacted to ensure that follow up with the participant takes place.

## **13. SAFETY ASSESSMENT & MONITORING**

### **13.1 Assessment of Adverse Events**

Information will be collected regarding all adverse events (AE) that occur from the time of randomisation until maternal and neonatal primary hospital discharge after delivery. Any events reported in the six week post-partum questionnaire will be reviewed for their potential to fulfil adverse event criteria and reported if necessary.

The general definition of an AE is any unfavourable and unintended change in structure, function, or chemistry of the body temporally associated with the study drug whether or not considered related to the use of the study medication. Worsening of a pre-existing condition which is temporally associated with the use of the study medication may also be considered an AE.

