## **Expectedness of SAEs**

SAEs must also be assessed for expectedness in this clinical setting. The investigator is responsible for determining whether an SAE is expected or not based on the underlying pregnancy and CS delivery, the pre-existing condition of the fetus/neonate, and the published reference safety information for betamethasone (including this protocol and the summary of product characteristics, such as the MedSafe Data Sheet). An unexpected adverse event/reaction is one that is not reported in the reference safety information, is more severe than previously reported or is not reasonably explained by the underlying condition.

Review of all of the known information about the SAE should conclude one of the following:

Expected Events:

- Expected Unrelated Event: the SAE is expected based on the known information about the study drug or the underlying condition and is not considered to be related to the study drug. This is referred to as an Expected SAE.
- Expected Related Event: an SAE which the Investigator considers possibly, probably or definitely related to the study drug. This is referred to as a SAR – Serious Adverse Reaction.

Unexpected Events:

- Unexpected Unrelated Event: the SAE is unexpected based on the known information about the drug or the underlying condition and is not considered related to the study drug. This is referred to as an Unexpected SAE.
- Unexpected Related Event: the SAE is unexpected based on the known information about the drug or the underlying condition and is considered possibly, probably or definitely related to the study drug. This is referred to as a SUSAR – Suspected Unexpected Serious Adverse Reaction.

Fetal or neonatal death and maternal death and maternal life-threatening complications should always be considered unexpected events in this population and require immediate reporting.

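### The AE window ends at primary hospital discharge, no SAE end date is stated, and nothing routes serious events found in the six-week record review into SAE reporting

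*Protocol*

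**What the plan says.** Section 13.1 sets the adverse event window: all AEs that "occur from the time of randomisation until maternal and neonatal primary hospital discharge after delivery". It adds one provision for the time after discharge: "Any events reported in the six week post-partum questionnaire will be reviewed for their potential to fulfil adverse event criteria and reported if necessary". Section 12.1.9 fixes when that form goes out: "Participants will be sent the following questionnaires six weeks after delivery", by email or, on request, by post.

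Section 12.1.8 takes outcomes from the records of mother and baby and gives them a longer window: "Maternal outcome data will be collected until six weeks after birth. Neonatal outcome data will be collected until six weeks after birth".

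Section 13.2 lists the serious adverse events. They include maternal, fetal and neonatal death, maternal life-threatening events and major haemorrhage before or after birth. No time window is attached. The part of 13.3 on expectedness says: "Fetal or neonatal death and maternal death and maternal life-threatening complications should always be considered unexpected events in this population and require immediate reporting". Section 13.4 makes serious adverse reactions, unexpected SAEs and SUSARs reportable within 24 hours of the site learning of them; expected SAEs go in the CRF only.

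Section 13.5 has the Safety Monitoring Committee review all SAEs. Section 13.6 plans no interim analyses and has the DMC review AEs and SAEs, with the power to recommend early termination.

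**The concern.** Two follow-up windows run side by side and are not joined. Outcomes are followed in the records to six weeks; adverse events are followed to primary discharge, and after that 13.1 mentions only a form the mother fills in. Several of the listed SAEs can occur after discharge: neonatal death, maternal death, a life-threatening maternal event, a late major haemorrhage.

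The named route works worst for these. A mother who has died cannot return a form, and a bereaved or seriously ill mother may not. Even a prompt return brings the event to light about six weeks after the birth, which fits poorly with a duty of immediate reporting.

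What is at stake is the completeness and timeliness of the SAE count. With no interim analysis planned, the adverse event review is the basis the protocol gives the DMC for recommending a stop. Section 4.2 also names maternal infection as a possible risk of the drug that the trial is meant to quantify, and severe infection can present after the mother has gone home.

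**Working it through.** No arithmetic applies: the point turns on windows and reporting routes, and the protocol states no figure to reproduce. The check is to set the sections side by side and follow a serious event that occurs after discharge but before six weeks.

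1. **Is it inside the AE window?** No. The window in 13.1 ends when both mother and baby have had their primary discharge. It lasts longer if the baby stays in hospital, but it still ends there.

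2. **Is there a separate SAE window?** No. Sections 13.2 to 13.4 give definitions, grading, expectedness and reporting times, but no start or end date. SAEs are a subset of AEs, so the only stated window is the one in 13.1, and a site can reasonably apply it to SAEs. The questionnaire sentence supports that reading: if events after discharge were already in scope, it would not be needed. The lack of any time limit in the expectedness rule and in 13.4 supports the opposite reading. Both are tenable.

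3. **If a site hears of the event, must it report?** On the second reading, yes. Deaths and maternal life-threatening complications are always treated as unexpected, and 13.4 starts its 24-hour clock when the site becomes aware.

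4. **Does anything make the site aware?** The record review in 12.1.8 could, since it runs to six weeks for mother and baby. But that section describes outcome data. Neither it nor section 13 says that an SAE-qualifying event seen there must be assessed and reported as one. The questionnaire could also bring it to light, if returned.

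5. **Would the event be caught as an outcome instead?**
   - Infection, largely yes. Late onset neonatal infection and maternal infection needing postpartum antibiotics are secondary outcomes in 15.2. A severe case could still be recorded there without reaching the committee that reviews SAEs.
   - Death, no. It appears in the SAE list but in neither 15.1 nor 15.2. The survival check in 6.3 applies only where a participant has completely withdrawn consent.

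So a death after discharge has a duty to report that depends on awareness, no stated duty to look for it as a safety event, and no outcome field that would record it by default.

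**The case against.** The strongest reply is that the reporting duty already covers these events. Section 13.4 is triggered by awareness, has no discharge cut-off and does not mention the questionnaire. The expectedness rule singles out deaths and maternal life-threatening complications for immediate reporting. A site reviewing records to six weeks can learn of such an event without any form. All of this stands. A reader might infer from 13.1 that a death or serious event after discharge reaches the safety system only if the mother returns her questionnaire, or that SAE collection is expressly closed at discharge. The protocol supports neither: 13.1 speaks of adverse events in general, and the later sections repeat no limit.

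A second reply is that ending routine AE capture at discharge after a two-dose antenatal course is a legitimate design choice. That also stands, for non-serious events.

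A third is that maternal infection is a secondary outcome, with maternal outcomes followed to six weeks, so estimating its rate does not depend on the AE window. That is right, and the point does not rest on it.

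What these replies leave unanswered is that a duty on awareness does not require anyone to look, and that the protocol does not say which window governs SAEs. Sites could apply it differently.

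**Conclusion.** The point holds as a gap in the safety-reporting rules. The AE window stops at primary discharge, the SAE window is unstated, and the six-week record review is not linked to SAE reporting. A death or serious event after discharge could therefore be reported late or inconsistently, or be missing from the count that the Safety Monitoring Committee and DMC see. It does not follow that such events would be missed as a rule.

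The size cannot be given from the protocol. It states no length of stay, no expected questionnaire response and no rate of serious events after discharge. Any percentage would rest on assumed values, and a share of follow-up time is not a share of events. The conclusion needs no such figure. It rests on the text of 12.1.8, 13.1 to 13.4 and 15, and on the view that a site could in good faith apply 13.1 to SAEs.

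Sample size, power, alpha and the analysis of the co-primary outcomes are untouched. The change is worth making because the gap concerns the gravest events and is cheap to close.

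**What to change.** In 13.1, state that SAEs in mother and baby are collected from randomisation until six weeks after birth, matching 12.1.8. Add that any event meeting the SAE criteria, whether found in the six-week record review or in the questionnaire, is assessed and reported under 13.4, with the clock running from site awareness. Non-serious AE collection may still end at primary discharge.

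The cost is a wording change, an SAE prompt on whichever form holds the six-week outcome data, and a few more SAE reports for sites. No new visit or data source is needed, since the records are already used to six weeks.

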### **13.2 Serious Adverse Events**

In this trial the following will be considered serious adverse events:

- Maternal death
- Fetal death
- Neonatal death
- Maternal life threatening event
- Maternal persistent or significant disability or incapacity
- Major antepartum or postpartum haemorrhage (>1500 mL)
- Other medically important event considered to be an SAE by Investigator

Important medical events that may not result in death, threat to life, or not require hospitalisation may be also considered an SAE when, based upon appropriate medical judgment, the event may jeopardise the participant and may require medical or surgical intervention to prevent one of the outcomes listed above. The term life threatening here refers to an event in which the patient is at risk of death at the time of the event; it does not refer to an event that might hypothetically cause death if it was more severe.

In the event of maternal SAE that may impact on the mother's ability to provide consent after birth other parent or guardian consent should be obtained for the baby/babies. If this consent is delayed neonatal blood glucose monitoring must be performed for safety reasons and consent should be sought as soon as this is appropriate.

### **13.3 Investigator Review of AEs/SAEs:**

The maximum intensity of adverse and serious adverse events must be assessed by an investigator. The following are the minimum parameters to be collected for each event:

- Maximum intensity: mild, moderate, severe, life threatening, death. Severity criteria based on the Common Terminology Criteria for Adverse Events (CTCAE), and adapted for the neonatal population should be used in this assessment, as per table 1 below.
- Duration. The start and stop dates will be identified and recorded.
- Action taken in regards to the study drug. Does the event cause the study medication to be temporarily or permanently discontinued?
- Relationship to study medication. The investigator will determine if the study medication contributed to the AE/SAE. Factors to consider:

Exposure: Was participant exposed to the study medication?

Likely cause: Is the event reasonably explained by aetiology such as underlying disease or other environmental factors?

Re-challenge: Was the participant re-exposed to the study medication? If yes, did the event recur or worsen?

Consistency with the study medication: Is the clinical/pathology presentation of the event consistent with previous knowledge regarding the study medication?

- Details of any treatment given.

**Table 1:** Adverse event severity criteria.

	Mild	Moderate	Severe	Life threatening	Death
Adult/ paediatric	Mild; asymptomatic or mild symptoms; clinical or diagnostic observations only; intervention not indicated.	Moderate; minimal, local or non-invasive intervention indicated; limiting age-appropriate instrumental activities of daily living.	Severe or medically significant but not immediately life threatening; hospitalisation or prolongation of hospitalisation indicated; disabling; limiting self care activities of daily living.	Life-threatening consequences; urgent intervention indicated.	Death related to AE.
Neonate	Mild; asymptomatic or mild symptoms; clinical or diagnostic observations only; no change in baseline age-appropriate behaviour*; no change in baseline care or monitoring indicated.	Moderate; resulting in minor changes of baseline age appropriate behaviour*; requiring minor changes in baseline care or monitoring. †	Severe; resulting in major changes of baseline age-appropriate behaviour* or non-life-threatening changes in basal physiological processes‡; requiring major change in baseline care or monitoring. §	Life threatening; resulting in life-threatening changes in basal physiological processes‡; requiring urgent major change in baseline care. §	Death related to AE.

\*Age-appropriate behaviour refers to oral feeding behaviour, voluntary movements and activity, crying pattern, social interactions and perception of pain.

†Minor care changes constitute: brief, local, non-invasive or symptomatic treatments.

‡Basal physiological processes refer to oxygenation, ventilation, tissue perfusion, metabolic stability and organ functioning.

§Major care changes constitute: surgery, addition of long-term treatment, upscaling care level.

## **Expectedness of SAEs**

SAEs must also be assessed for expectedness in this clinical setting. The investigator is responsible for determining whether an SAE is expected or not based on the underlying pregnancy and CS delivery, the pre-existing condition of the fetus/neonate, and the published reference safety information for betamethasone (including this protocol and the summary of product characteristics, such as the MedSafe Data Sheet). An unexpected adverse event/reaction is one that is not reported in the reference safety information, is more severe than previously reported or is not reasonably explained by the underlying condition.

Review of all of the known information about the SAE should conclude one of the following:

Expected Events:

- Expected Unrelated Event: the SAE is expected based on the known information about the study drug or the underlying condition and is not considered to be related to the study drug. This is referred to as an Expected SAE.
- Expected Related Event: an SAE which the Investigator considers possibly, probably or definitely related to the study drug. This is referred to as a SAR – Serious Adverse Reaction.

Unexpected Events:

- Unexpected Unrelated Event: the SAE is unexpected based on the known information about the drug or the underlying condition and is not considered related to the study drug. This is referred to as an Unexpected SAE.
- Unexpected Related Event: the SAE is unexpected based on the known information about the drug or the underlying condition and is considered possibly, probably or definitely related to the study drug. This is referred to as a SUSAR – Suspected Unexpected Serious Adverse Reaction.

Fetal or neonatal death and maternal death and maternal life-threatening complications should always be considered unexpected events in this population and require immediate reporting.

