### **13.4 Procedure for AE and SAE Reporting**

All AEs and SAEs must be documented in the participant's CRF. SAEs may also require immediate reporting by the site, as below:

Actions for SAEs:

1. Report immediately, within 24 hours of becoming aware of the event:
  - SAR – suspected adverse reaction.
  - Unexpected SAE.

- SUSAR – Suspected Unexpected Serious Adverse Reaction.
2. Documented in the CRF only (do not require immediate reporting):
- Expected SAE.

Unexpected SAEs, SUSARs and SARs will be reported to the C\*STEROID DMC, regulatory authorities and ethics committees, as required.

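### The definition of an unexpected SAE conflicts with the classification bullets below it, so some SAEs judged unrelated are told both to stay in the CRF and to be reported within 24 hours.

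*Protocol*

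**What the plan says.** Section 13.3, under Expectedness of SAEs, first gives a definition: "An unexpected adverse event/reaction is one that is not reported in the reference safety information, is more severe than previously reported". A third alternative completes the sentence, so that it ends: "is more severe than previously reported or is not reasonably explained by the underlying condition".

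Four bullets follow, and the investigator must settle on one of them:

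- *Expected, unrelated* (Expected SAE): "the SAE is expected based on the known information about the study drug or the underlying condition and is not considered to be related".
- *Expected, related* (SAR): "Expected Related Event: an SAE which the Investigator considers possibly, probably or definitely related to the study drug".
- *Unexpected, unrelated* (Unexpected SAE): "the SAE is unexpected based on the known information about the drug or the underlying condition", and not considered related.
- *Unexpected, related* (SUSAR): the same wording on unexpectedness, and considered related.

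An override closes the section. Fetal, neonatal and maternal deaths and maternal life-threatening complications always count as unexpected.

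Section 13.4 attaches the actions. SARs, Unexpected SAEs and SUSARs are reported within 24 hours and passed on to the DMC, regulators and ethics committees as required. Expected SAEs are "Documented in the CRF only (do not require immediate reporting").

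Section 13.2 lists the event types that count as serious. One of them is "Major antepartum or postpartum haemorrhage (>1500 mL").

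**The concern.** The definition and the bullets combine the same facts in opposite ways. Under the definition, failing any one condition makes an event unexpected. Under the expected-unrelated bullet, satisfying either of two conditions makes it expected. An event that satisfies one and fails another falls on both sides.

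For an unrelated SAE, this classification alone decides between a CRF entry and a 24-hour report with onward routing. Investigators at many sites in two countries make the call. Two sites that both follow the protocol faithfully could route the same event differently, and a tally of unexpected SAEs would partly reflect which sentence each site applied.

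**Working it through.** The protocol states no figure to reproduce, so this is a check of logic.

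Let R = the event is in the reference safety information; S = it is more severe than reported there (meaningful only if R holds); C = it is reasonably explained by the underlying condition.

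- Definition: unexpected = (not R) or S or (not C).
- Expected-unrelated bullet: expected = (R and not S) or C. The bullet does not mention severity; 'and not S' is my reading of being expected from the drug information.

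| State | Definition says unexpected | Bullet says expected |
|---|---|---|
| 1. not R, not C | yes | no |
| 2. not R, C | yes | yes |
| 3. R, not S, not C | yes | yes |
| 4. R, not S, C | no | yes |
| 5. R, S, not C | yes | no |
| 6. R, S, C | yes | yes |

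The definition makes 5 of 6 states unexpected and the bullet makes 4 of 6 expected. Three states (2, 3 and 6) are both. If listing alone is taken to suffice, so that expected = R or C, state 5 joins them and 4 of 6 are both. State 2 is in conflict on either reading.

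**The bullets against each other.** Taking the 'or' in the unexpected-unrelated bullet literally gives unexpected = (not R or S) or (not C), which is the definition again. The two unrelated bullets therefore overlap in the same states, and correcting the definition alone would leave that overlap.

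**Unrelated SAEs.** Take a haemorrhage over 1500 mL that is judged unrelated, is not life-threatening, is explained by the caesarean and is absent from the reference safety information. This is state 2. By the definition it is an Unexpected SAE, reported within 24 hours. By the expected-unrelated bullet it is an Expected SAE, entered in the CRF only.

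**Related SAEs.** SARs and SUSARs are both 24-hour reports under section 13.4, so the action is the same. The label is still unclear, for two reasons. The third condition makes a listed reaction unexpected whenever the underlying condition does not explain it (state 3), which nearly empties the SAR category. And the SAR bullet is worded by relatedness alone, so every SUSAR also fits it.

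**Override.** Deaths and maternal life-threatening complications are settled. The ambiguity is left with other haemorrhage, maternal disability and other medically important events.

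**The case against.** The best defence is the opening of the section, which asks for expectedness to be assessed in this clinical setting, from the pregnancy and caesarean, the fetal or neonatal condition and the reference safety information together. On that view an investigator would sensibly call a surgically explained bleed expected. The bullets can also be read as pooling the two sources, so that unexpected means known from neither. That removes the overlap between the bullets, but the definition then contradicts both of them. The opening sentence says what to weigh, not how to combine it; the next sentence supplies the rule, and that rule is the strict one.

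The section also counts the protocol itself as reference safety information, and section 13.2 names major haemorrhage. But that is a list of what is serious. It includes deaths, which the override makes always unexpected, so it cannot serve as a list of expected events.

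Several stronger conclusions might be inferred, and the protocol does not support them:

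- *That expected SAEs drop out of sight, or that this is the only ongoing safety trigger.* Under section 13.5 the Safety Monitoring Committee reviews all SAEs and reports to the Trial Steering Committee, which takes safety issues to the DMC. Under section 13.6 the DMC reviews adverse and serious adverse events and can recommend stopping.
- *That related SAEs also get contradictory reporting instructions.* They do not; only the label differs.
- *That the number of affected events can be given.* One could assume a haemorrhage rate of 1% to 3% among about 2548 / 1.02 = 2498 mothers and reach 25 to 75. The rate is not in the protocol, and the count does not remove life-threatening bleeds, which the override settles, or bleeds judged related.
- *That 3 of 6 states measures the size.* The states are unweighted, and the conflict over action concerns unrelated SAEs only.
- *That the comparison of arms is biased.* Expectedness is not an outcome, allocation is blinded and randomisation is stratified by site.

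**Conclusion.** The contradiction stands, within limits. For SAEs judged unrelated that are neither deaths nor maternal life-threatening complications, sections 13.3 and 13.4 can require both CRF-only documentation and a 24-hour report. For related SAEs the ambiguity is one of label. The effect is on the speed, routing and consistent classification of reports across sites; the primary analysis and sample size are not affected.

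The number of events affected cannot be derived from the protocol. The haemorrhage example assumes that the event is absent from the reference safety information and is judged unrelated. The contradiction itself rests only on the wording. Because the stated rule gives conflicting instructions for a named type of SAE, it is an error in the text rather than detail left to another document, and it is worth correcting.

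**What to change.** Reconcile the definition and all four bullets in section 13.3 with each other and with section 13.4:

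- **Related SAEs:** assess against the reference safety information. Unexpected (SUSAR) if not listed, or more severe than listed; otherwise expected (SAR). Write this criterion into the SAR bullet, which has none.
- **Unrelated SAEs:** assess against the pregnancy, the caesarean and the fetal or neonatal condition. Unexpected if not reasonably explained by these; otherwise expected.
- **Override:** keep it as it stands.

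Each SAE then falls into exactly one category with one action. The cost is a short amendment, matching guidance for completing SAE forms, and a re-check of SAEs already classified. No new data or staff are needed.
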